#### **9.4.4. Fasting**

There is no requirement for fasting in this study.

## 10. TREATMENT OF SUBJECTS

### 10.1. Description of Study Drug

**Table 6: Investigational Product**

	Investigational Product
Product Name:	EXN407
Dosage Form:	EXN407 ophthalmic solution is supplied in single-use low density polyethylene (LDPE) BFS ampoules, which allow for product administration directly to the eye
Unit-Dose	EXN407 will be provided at three concentrations: 0.5 mg/mL (0.05%) 1.0 mg/mL (0.1%) 1.5 mg/mL (0.15%)
Route of Administration	For topical ophthalmic administration by eye drop
Physical Description	EXN407 ophthalmic solution is presented as a preservative-free, sterile, clear, colorless solution
Manufacturer	[REDACTED]

### 10.2. Concomitant Medications

All medications, including over-the-counter (OTC) medications, vitamins, and herbal supplements, taken during the 30 days prior to the first study drug administration will be recorded and reviewed by the Investigator to determine whether the subject is suitable for inclusion in the study.

The use of any IP or investigational medical device within 30 days prior to Screening is prohibited. Additional restrictions relating to concomitant medication use are outlined in [Section 9.4](#).

All medications, including OTC medications, vitamins, and herbal supplements, taken by subjects during the course of the study will be recorded in the eCRF and coded using the most current WHO drug dictionary available at [REDACTED]. Prior and concomitant medications will be listed by subject and summarized by anatomical therapeutic chemical (ATC) and Preferred Term (PT).

### 10.3. Treatment Compliance

Study drug will be administered at the clinic under supervision and instruction of assigned clinical staff at the day of first dosing, and on days where a pre-dose PK sample is required

(escalation cohorts Day 3, expansion cohort Day 8). Subjects will self-administer their IP without supervision thereafter.

#### **10.4. Treatment Tolerability Assessment**

Subjects will be asked by the Investigator or delegated study staff to provide a verbal assessment of the tolerability of the treatment administration via dropper. They will be asked to describe the level of comfort / discomfort on a scale of 0-10, with 0 being no discomfort and 10 being very uncomfortable. The subject will be asked immediately following dosing, then again at 1 and 2 minutes following dosing.

#### **10.5. Masking (Blinding)**

Masking procedures for the study will be described in detail in the Randomization Plan.

The Sponsor study team, Investigator, MM, study personnel, and subjects are not to make any effort to determine which study drug therapy is being received.

Only in the case of an emergency, when knowledge of the study drug is essential for the clinical management or welfare of a specific subject, the Investigator may unblind a subject's treatment assignment via Medidata Randomization and Trial Supply Management (RTSM). However, prior to any unblinding, the Investigator is strongly advised to discuss options with the MM, Sponsor or appropriate study personnel. The Investigator will record in source documentation, the date and reason for revealing the blinded treatment assignment for that subject and the names and roles of personnel unblinded.

As soon as possible, and without revealing the subject's study treatment assignment (unless important to the safety of subjects remaining in the study), the Investigator must notify the Sponsor if the blind is broken for any reason and the Investigator was unable to contact the Sponsor prior to unblinding.

If the Investigator considers an AE to be of such severity as to require immediate specific knowledge of the identity and dose of the relevant product, the Investigator may break the study code for that subject.

Randomization codebreak procedures are provided in [Section 14.10](#).

All unblinding events must be reported to the MM and [REDACTED] promptly.

## **11. STUDY DRUG MATERIALS AND MANAGEMENT**

### **11.1. Study Drug**

The Sponsor will supply the study drug (both EXN407 and vehicle) to the investigational site. The study drug provided for this study was manufactured under current Good Manufacturing Practices (cGMP) and is suitable for human use.

### **11.2. Study Drug Packaging and Labelling**

The Sponsor is responsible for the preparation and labelling and providing details of batch numbers, safety and stability data.

The study drug will be labelled in accordance with local regulatory requirements and will be shipped at a temperature of 2-8°C.

### **11.3. Study Drug Storage**

Upon receipt, the study drug must be stored at 2-8°C.

The Investigator or designee will be fully responsible for the security, accessibility and storage of the study drug while it is at the investigational facility.

### **11.4. Study Drug Preparation**

EXN407 topical ophthalmic solution and placebo to match are presented for the proposed clinical study in single-use LDPE BFS ampoules, which allow for product administration directly to the eye. Each ampoule contains a nominal volume of 0.45 mL. A day pack of five ampoules is provided in a foil overwrap. Procedures relating to study drug preparation and dispensing are outlined in the Pharmacy Manual.

### **11.5. Administration**

The Investigator or designee is responsible for the education of study staff and subjects as to the correct administration of the study drug, and subjects (or a subject's partner where applicable) will self-administer/administer the study drug following instruction from the Investigator or their delegate.

### **11.6. Study Drug Accountability**

A record will be maintained by the investigational site that will account for all dispensing and return of any used and unused study drug. At the end of the study, the study drug will be reconciled, and a copy of the record given to the study monitor.

### **11.7. Study Drug Handling and Disposal**

On completion of the study, any surplus study drug supplies will be destroyed following site standard operating procedure for drug destruction, upon receipt of written approval from the Sponsor. Evidence of the destruction of any surplus study drug will be supplied to the study monitor. If no supplies remain, this will be documented in the dispensing record.

## 12. STUDY SCHEDULE

A Schedule of Assessments is provided in [Table 5](#).

Where possible, assessments should be conducted in order of least invasive to most invasive.

### 12.1. Visit 1A/1E - Screening (Day -28 to Day -7)

Prior to enrolling into the study, and before the performance of any study procedures, potential subjects will attend a Screening Visit at which time they will be provided with full information concerning details of the study assessments and procedures. They will also be provided with an Informed Consent Form (ICF). Prior to being asked to sign the consent form, subjects will be given time to review study information and ask any questions.

After the consent form is signed, Screening assessments will be carried out as follows:

- Documentation of Demographics
- Documentation of medical, surgical and ocular history
- Documentation of Prior and Concomitant Medications
- Height and weight measurements, which will be used to automatically calculate body mass index (BMI) upon entry to the eCRF
- Vital Sign Measurements - systolic and diastolic blood pressure (BP), heart rate, respiratory rate, body temperature
- Physical Exam - Complete physical examination including: general appearance, head, ears, eyes, nose, throat, thyroid, chest (heart, lungs), abdomen, skin, neurological, extremities, back, neck, musculoskeletal, and lymph nodes
- Single 12-lead ECG
- Collection of urine for urinalysis
- Urine Pregnancy test (WOCBP only)
- FSH testing (for postmenopausal subjects only)
- Collection of blood for hematology, serum chemistry and coagulation assessments
- Ophthalmic Exam/ Ophthalmoscopy
- SD-OCT
- BCVA – to be done prior to all procedures requiring pupil dilation: FFA, etc.
- Corneal endothelial cell count (dose expansion cohort only [Visit 1E]; documented assessment within the 6 months prior to baseline is acceptable; however, post-treatment assessment must be conducted using the same equipment)
- CFP
- Tonometry to measure IOP
- Corneal pachymetry

- FFA
- Investigator review of all eligibility criteria

### **12.1.1. Identification of Study Eye and Contralateral Eye**

Following completion of the ophthalmologic assessments, including SD-OCT and BCVA, the Investigator should identify the eye in which evident center involved DME is present with a CMT between 280-420  $\mu\text{m}$  as determined by SD-OCT. All SD-OCT assessments for a subject should be taken with the same make and model of equipment throughout the duration of the study.

If both eyes qualify on the basis of evident DME with a CMT between 280-420  $\mu\text{m}$ , and BCVA better than or equal to a 69 ETDRS score (an approximate Snellen equivalent of 20/40 or 6/12) then the Investigator should choose the eye with the worse (greater) CMT as the study eye. If CMT is the same in both eyes then the eye with the worse visual function as assessed by BCVA will be selected as the study eye. If both eyes have the same BCVA then the right eye will be selected.

All protocol evaluations will also be completed on the non-dosed contralateral eye. No vehicle-control or other study treatments will be administered to the contralateral eye.

### **12.2. Run-in Period (Post-Screening to Day -1 Pre-randomization)**

Subjects that meet all eligibility criteria at Screening as assessed by the evaluating Investigator will enter a run-in period (from post-Screening to Day -1) where the subject (or subject's partner as applicable) will administer eye drops BID using Systane Ultra UD droppers. The run-in period serves to familiarize and train subjects in topical administration via eye dropper. There is no associated visit for this run-in period.

This is to mean that upon completion of the Screening procedures, if the Investigator considers the subject eligible based upon all results in hand, the run-in period may commence immediately. The Investigator does not need to await return of external reports. The Investigator will have their assessment of CMT on hand for initial determination of eligibility and study eye, before the subject enters run-in. There is no concern regarding use of the Systane Ultra UD eye drops in patients and full eligibility cannot be determined until subjects attend the baseline visit and confirm proficiency in administration of eye drops.

Upon initiating the subject's run-in period, sites should inform [REDACTED] that the Investigator has initially assessed the patient as eligible (pending remaining reports and run-in proficiency).

A central reading facility (EyeKor) is being used to determine eligibility based upon center involved DME (in particular CMT reading). The turnaround time for this is 3 business days. The run-in period can be shortened to a minimum duration that allows for the results to be available for eligibility confirmation and randomization purposes at Visit 2A/2E.

For rescreening patients, if the patient is proficient in dropper use after their initial run-in, then a further run-in is not required.

## 12.3. Dose Escalation (A) Cohorts 1, 2, 3, etc.

### 12.3.1. Visit 2A - Day of First Dosing (Day 1)

#### 12.3.1.1. Before Dosing

Prior to dosing on Day 1, subjects will be randomized to one of the following treatments:

- EXN407
- Placebo (vehicle)

The following assessments should be performed prior to the administration of study drug unless otherwise noted:

- A verbal check by the Investigator that the subject experienced no issues with self-administration of Systane® Ultra UD eye drops during the run-in period
- Concomitant Medications
- Documentation of AEs since the Screening Visit (from time of consent)
- Weight measurement
- Vital Sign Measurements - systolic and diastolic BP, heart rate, respiratory rate, body temperature
- Physical Exam - Complete physical examination including: general appearance, head, ears, eyes, nose, throat, thyroid, chest (heart, lungs), abdomen, skin, neurological, extremities, back, neck, musculoskeletal, and lymph nodes
- Single 12 lead ECG
- Urine sample collected for urinalysis
- Urine Pregnancy test (WOCBP only)
- Blood draw for hematology, serum chemistry and coagulation
- Ophthalmic Exam/ Ophthalmoscopy
- SD-OCT
- BCVA
- Tonometry to measure IOP
- Corneal pachymetry
- Investigator review of all eligibility criteria

If not performed already during Screening, the following measures of retinal anatomy will be measured (required to be completed at least once prior to the subject's first dose of study drug):

- CFP

Any pre-dose assessment may be repeated if the results are considered unreliable or of unacceptable quality by the Investigator, or if the assessment could not be completed. In the case

of repeat assessments, the measure reflecting the highest level of visual function will be considered the baseline value unless regarded as an implausible reading in the opinion of the Investigator. Structural tests will be averaged and used as the baseline (pre-treatment value).

Following final review of all eligibility criteria and randomization the study drug will be dispensed ready for administration.

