#### *Screening*

During the Screening period, subjects will be assessed according to the eligibility criteria. Measures of retinal structure and visual function including SD-OCT and BCVA will be measured twice, for Screening and pre-dose on Day 1 (baseline), prior to each subject's first dose of the randomized study drug or vehicle. Other measures of retinal anatomy such as CFP will be measured at least once prior to the subject's first dose of study drug. Fluorescein fundus angiography will be assessed at the Screening Visit. Any pre-dose assessment may be repeated if the results are considered unreliable or of unacceptable quality by the Investigator, or if the assessment could not be completed. In the case of repeat assessments, the measure reflecting the highest level of visual function will be considered the baseline value unless regarded as an implausible reading in the opinion of the Investigator. Structural tests will be averaged and used as the baseline (pre-treatment value).

Subjects who meet all eligibility criteria will be enrolled into the study and will receive their first dose of the study drug on Day 1. EXN407 or vehicle will be instilled into the subject's study eye under supervision of the Investigator (or delegate). Subjects will be monitored for signs of irritation and inflammation for an initial period of 2 hours post-dose, for their first dose on Day 1 only. Subjects in dose escalation cohorts (numbered cohorts 1, 2, 3, etc.) will additionally return to the clinic at Day 3 and Day 4.

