#### 8.5.1.1. Individual Subject Stopping Criteria

Any of the following criteria will be considered as stopping criteria for the study eye in individual subjects:

- An increase from baseline in CMT  $\geq 75 \mu\text{m}$  when seen across two consecutive visits
- A loss of  $\geq 15$ -letters of vision as determined by ETDRS, from the best previous in-study BCVA, due to DME, with current BCVA not better than baseline
- A loss of  $\geq 10$ -letters of vision from best previous in-study BCVA (determined by ETDRS), due to DME, seen across two consecutive visits, with current BCVA score not better than baseline
- Persistent intolerable ocular irritation or redness
- Development of persistent corneal opacities or severe keratitis

- An  $\geq 10\%$  increase in corneal thickness in the study eye based on pachymetry assessed at a consistent time of day
- Intraocular pressure (IOP) increase of 12 mmHg or more (from baseline measurements) confirmed upon repeat testing
- Occurrence of any severe graded AE that is assessed by the Investigator to be related to study drug
- Occurrence of any serious adverse event assessed by the Investigator to be related to study drug
- If a subject's CMT is 420  $\mu\text{m}$  or less, the subject is withdrawn from the study if there is BOTH a loss of BCVA of  $\geq 10$  letters AND an increase in CMT of  $\geq 50 \mu\text{m}$
- If a subject's CMT is  $>420 \mu\text{m}$ , the subject is withdrawn if there was also EITHER a loss of BCVA of  $\geq 10$  letters OR an increase in CMT of  $\geq 50 \mu\text{m}$
- The Investigator believes it is in the best interest of the subject to discontinue study drug dosing and/or initiate an anti-VEGF or other rescue therapy.

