#### **18.3.6. Ophthalmologic Assessments**

Observations from ophthalmologic assessments will be summarized by protocol specified time point. Observed values and changes from baseline, summarized by treatment group, visit, and study and contralateral eye, will be presented (descriptive continuous data analysis).

The ophthalmologic assessments that will be summarized are listed below:

- Center-Subfield Macula Edema (center-subfield measure)
- Macular fluid volume
- BCVA using the ETDRS visual acuity scale
- FFA
- Corneal thickness based on pachymetry
- Corneal endothelial cell count
- CMT, macular volume, sub-retinal fluid, in the study and contralateral eye as assessed by SD-OCT
- Retinal anatomy as assessed by fluorescein angiography (leakage area) in the study eye and contralateral eye
- DRSS
- Proportion of subjects with a change from baseline value of  $\geq 5$ , 10 and 15 ETDRS letter score (gain or loss) in the study eye versus contralateral eye
- Proportion of subjects who require anti-VEGF therapy in the study and contralateral eye during the study and need for anti-VEGF in the study eye at Day 85 (Visit 7E) and follow-up, as data permit
- Observations via CFP
- Observations via SD-OCT. To evaluate the following ETDRS grid sectors :

- Central subfield
- Inner inferior, inner nasal, inner superior, and inner temporal sectors
- Outer inferior, outer nasal, outer superior, and outer temporal sectors
- Retinal thickness

- Automated Perimetry

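### The baseline rule for structural tests averages pre-dose readings without excluding one rejected for quality, so up to half of a bad scan's error can enter that eye's baseline

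*Combined protocol and SAP*

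**What the plan says.** Section 12.3.1.1 (Before Dosing, Visit 2A) sets out when a repeat is allowed: "Any pre-dose assessment may be repeated if the results are considered unreliable or of unacceptable quality by the Investigator". The only other trigger is an assessment that could not be completed. The Synopsis (Screening) gives the same rule without limiting it to the escalation cohorts.

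The handling then differs by type of test:

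- **Visual function:** "the measure reflecting the highest level of visual function will be considered the baseline value unless regarded as an implausible reading" in the Investigator's opinion.
- **Structure:** "Structural tests will be averaged and used as the baseline (pre-treatment value"). There is no exception for an implausible or rejected reading, and the text does not say how many readings are averaged or from which visits.

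The Synopsis also says: "Measures of retinal structure and visual function including SD-OCT and BCVA will be measured twice, for Screening and pre-dose on Day 1 (baseline").

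Baseline is then used in two places. Section 18.3.6 reports ophthalmologic data as "Observed values and changes from baseline, summarized by treatment group, visit, and study and contralateral eye, will be presented"; the list includes the center-subfield measure, macular fluid volume and corneal thickness, which are secondary safety endpoints in Section 7.2.2. Section 8.5.1.1 opens its individual stopping criteria with "An increase from baseline in CMT" of at least 75 µm across two consecutive visits, and Section 8.5.3 uses the same criterion for rescue eligibility.

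**The concern.** The only reasons given for a repeat are that the first attempt failed in some way. A rule that averages the failed attempt with its replacement undoes part of the purpose of repeating it. The plan recognises this for visual function, where an implausible value can be dropped, but gives no matching provision for structure.

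An error in baseline does not average out over visits. It moves every later change for that eye by the same amount in the same direction, so requiring two consecutive visits for the CMT criterion gives no protection. A rejected scan that read too high makes an unchanged eye look improved and hides part of a real thickening. One that read too low does the reverse. The escalation groups have three EXN407 subjects per dose, so a single eye can visibly move a dose-level mean.

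**Working it through.** The plan states no figure for this point: there is no baseline variance, repeat rate, power or alpha to reproduce. The check is therefore the weight that a rejected reading carries, followed through to the quantities that depend on baseline.

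**Inputs from the documents.** The CMT criterion is 75 µm (Section 8.5.1.1). The corneal-thickness criterion is 10% (same section, with no reference value named). There are 3 EXN407 subjects per escalation dose (Section 8.2). The expansion cohort is up to 40 at 2:1 (Section 6.4.3): 40 × 2/3 ≈ 27 active and 40 × 1/3 ≈ 13 vehicle.

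**Assumed inputs.** The error *e* of a rejected CMT reading is taken as 20 to 100 µm, and that of a rejected pachymetry reading as ±5%. Pachymetry is treated as a structural test; the plan does not list which tests it means.

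**Step 1: weight *w* of the rejected reading.**

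- Rejected reading plus one repeat, Screening not used: 1/2.
- Rejected reading plus two repeats, or Screening, rejected reading and repeat averaged together: 1/3.
- Screening averaged with the Day 1 mean of rejected and repeat: 1/4.
- Rejected reading dropped, or no value obtained: 0.

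**Step 2: baseline shift = *w* × *e*.** Each change from baseline for that eye moves by −*w* × *e*.

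| Weight | e = 20 µm | 40 µm | 60 µm | 100 µm |
|---|---|---|---|---|
| 1/2 | 10 | 20 | 30 | 50 |
| 1/3 | 6.7 | 13.3 | 20 | 33.3 |
| 1/4 | 5 | 10 | 15 | 25 |
| 0 | 0 | 0 | 0 | 0 |

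**Step 3: CMT criterion.** The true rise at which 75 µm is reached is 75 ± *w* × *e*. With *e* = 60 µm and *w* = 1/2, it is 75 − 30 = 45 µm if the rejected scan read low, and 75 + 30 = 105 µm if it read high. At *w* = 1/4 the figures are 60 and 90 µm.

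**Step 4: group means.** One such subject (*e* = 60, *w* = 1/2, shift 30 µm) moves the mean change by 30/3 = 10 µm in an escalation dose group, 30/13 = 2.3 µm in the expansion vehicle group and 30/27 = 1.1 µm in the expansion active group.

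**Step 5: pachymetry, only if baseline is the reference.** The true rise that meets 10% is 1.10 × (1 + *w* × *r*) − 1, where *r* is the relative error. At *w* = 1/2 and *r* = ±5%: 1.10 × 0.975 − 1 = 7.25%, or 1.10 × 1.025 − 1 = 12.75%.

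**Step 6: purely random error.** Suppose the rejected scan's SD is *k* times that of a good scan. The variance of the two-reading average, relative to the replacement alone, is (1 + *k*²)/4. This is 0.81 at *k* = 1.5, 1.25 at *k* = 2 and 2.5 at *k* = 3. It exceeds 1 only when *k* > √3 ≈ 1.73.

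**The case against.** Several counter-arguments have force.

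- **The sentence does not say which readings are averaged.** SD-OCT is planned at both Screening and Day 1, so the intended meaning may be the mean of those two. This stands as a possible reading, but it does not settle the matter: it still does not say whether a rejected Day 1 scan is dropped.
- **A reader might infer that half of the error always enters, or that all change-from-baseline results are affected.** The documents support neither. One half needs exactly one rejected value, one repeat and no Screening value. A test that could not be completed may leave nothing to average. Eyes without a repeat are untouched, and no repeat rate is given.
- **Averaging can help.** If the rejected scan's error is random and less than 1.73 times that of a good scan, the average is the more precise baseline. This is true, but a scan bad enough to reject may well carry a larger or systematic error.
- **A reader might infer that the shift alters dosing in the escalation cohorts.** Scheduled SD-OCT and pachymetry after baseline fall there on Day 8 and Day 36, after the seven days of dosing. At scheduled visits the shift could change only whether a subject counts as meeting a criterion. Consequences for dosing could arise in the expansion cohort. There the Visit 2E text (Section 12.4.1.1) does not repeat the rule, and only the Synopsis carries it.
- **A reader might infer a bias between arms.** The readings are pre-dose in a randomized, masked study, so the error has no stated direction by treatment. The analysis is also descriptive, and the primary endpoint is ocular adverse events.
- **The SAP may resolve it.** Section 18 defers detailed methods to a SAP whose text is not among the documents reviewed, so a suitable definition there cannot be ruled out. Section 18 itself defines no baseline. Section 12.2 gives the central reading facility a role in eligibility and does not say that it removes poor scans from baseline.

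**Conclusion.** The point holds in limited form. Followed as written, the rule lets a structural reading rejected for quality into baseline at a weight of up to one half, while the parallel rule for visual function allows an implausible reading to be set aside. This is a stated rule that can give a worse baseline than simply using the replacement.

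The effect is confined to eyes with a repeat whose rejected reading gave a value. Within them it could be material: 5 to 50 µm in CMT over the assumed range of errors and weights 1/4 to 1/2, against a 75 µm criterion expressly measured from baseline. For group summaries it matters mainly in the three-subject escalation groups and little in the expansion cohort. The size of the reading error is an assumption throughout. The effect on the corneal-thickness criterion also depends on baseline being its unstated reference. It should be corrected because the remedy is specific and nearly free.

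**What to change.** In Section 12.3.1.1, the Synopsis (Screening) and the SAP, define the structural baseline along these lines: *Baseline is the mean of the acceptable-quality readings from [Screening, Day 1, or both, to be stated]. A reading that was repeated because of its reliability or quality is left out of the mean and shown in the listings only. The reason for rejection is recorded before randomization.*

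Recording the rejection before randomization keeps the choice of readings independent of treatment and of later results. Section 12.4.1.1 (Visit 2E) should carry or refer to the same rule so that both parts of the study use one definition, and Section 18 should contain the baseline definition it now lacks. The sponsor should also state the reference value for the corneal-thickness criterion.

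The cost is one sentence in each place and a quality flag on the eCRF. No assessment is added and no clinical threshold changes. With the rejected reading at weight zero, its error no longer enters baseline.
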